## **Abstract**

This study is designed to test the performance and demonstrate effectiveness of the NOWDiagnostics, Inc. (NOWDx) COVID-19 Test for the detection of antibodies in response to SARS-CoV-2 infection. ADEXUSDx® is the registered brand of the COVID-19 antibody test intended for point of care (POC), also known as CLIA waived, use.

The study will be performed by CLIA waived site operators, representative of intended users of the ADEXUSDx® COVID-19 Test, to support U.S. Food and Drug Administration (FDA) Emergency Use Authorization (EUA) of the device. Site operators will perform tests on enrolled participants via finger stick method with capillary blood.

Venous whole blood samples will also be collected from participants per local standard phlebotomy procedures at the study sites and will be used by site operators to perform tests via transfer device method.

## **Background Information and Rationale**

On February 4, 2020, the Secretary of Health and Human Services (HHS) determined that there is a public health emergency and that circumstances exist justifying the authorization of emergency use of in vitro diagnostics for detection and/or diagnosis of the novel coronavirus (SARS-CoV-2). Rapid detection of coronavirus 2019 (COVID-19) cases in the United States requires wide availability of diagnostic testing to control the emergence of this rapidly spreading, severe illness. In light of this public health emergency, NOWDiagnostics Inc. elected to develop and manufacture a COVID-19 serological diagnostic test that identifies total immunoglobulin (IgM, IgG, and IgA) to SARS-CoV-2. The FDA has issued guidance describing a policy for laboratories and commercial manufacturers to help accelerate the use of tests developed in order to achieve more rapid and widespread testing capacity in the United States. According to said FDA guidance, clinical accuracy should be established on human specimens from patients with microbiologically confirmed COVID-19 infection using an emergency use authorized assay in addition to human specimens from patients negative for COVID-19 using an emergency use authorized assay.

## **Study Objectives**

The purpose of this study is to generate NOWDx COVID-19 Test performance data to support FDA POC EUA of the device with capillary blood from a finger stick, and POC EUA of the device with venous whole blood from a blood draw.

## **Study Duration, Planned Enrollment, and Number of Sites**

Studies will be performed for the period July 20, 2020 through Aug 31, 2020. Total planned enrollment is 60 study participants. Studies will be performed at CLIA waived study sites. Participants will be varied in age, gender diverse, ethnically and racially diverse, economically diverse, and with different levels of education.

## **Study Population, Inclusion and Exclusion Criteria**

The following cohorts will be prospectively recruited and enrolled in this study:

### **Clinical Study Cohorts:**

- Cohort: Persons who have tested positive for COVID-19 with an emergency use authorized molecular (PCR) test and can furnish said test report;  $\geq 7$  days post emergency use authorized molecular (PCR) test
  - n=30

Title: NOWDx COVID-19 EUA Blood Test CLIA Waiver Trial

Sponsor: NOWDiagnostics, Inc.

- Inclusion criteria: Persons who have tested positive for COVID-19 with an emergency use authorized molecular (PCR) test and can furnish said test report; ≥ 7 days post emergency use authorized molecular (PCR) test
- Exclusion criteria: persons <18 years old; persons with limited or no reading skills; persons who have previously participated in a NOWDx study; < 7 days post emergency use authorized molecular (PCR) test
- Cohort: Persons who have tested negative for COVID-19 with an emergency use authorized molecular (PCR) test and can furnish said test report; 0-6 days post emergency use authorized molecular (PCR) test
  - n=30
  - Inclusion criteria: Persons who have tested negative for COVID-19 with an emergency use authorized molecular (PCR) test and can furnish said test report; 0-6 days post emergency use authorized molecular (PCR) test
  - Exclusion criteria: persons <18 years old; persons with limited or no reading skills; persons who have previously participated in a NOWDx study; > 6 days post emergency use authorized molecular (PCR) test

Any person who does not meet inclusion criteria will be declined participation in the study. If a person is eligible for study participation in a cohort that has met the enrollment quota designated by NOWDx, he or she will be declined participation in the study.

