
### **Study Procedures**

Herein, we present study procedures for the 'Clinical Study':

Title: NOWDx COVID-19 EUA Blood Test CLIA Waiver Trial

Sponsor: NOWDiagnostics, Inc.

- Site operator 1 will create a participant ID.  
*Note: Specific cohort assignment will not be made until study visit is complete.*
- Site operator 1 will provide the participant with a demographic survey to complete (see **Appendix C. Demographic Survey of Participant**). Participant will complete the survey.
- Site operator 1 will read the Finger Stick Method (Waived) Instructions For Use and perform the ADEXUSDx® COVID-19 Test on the participant according to the instructions.
- Site operator 1 will complete a Case Report Form of Site Operator 1.
- Site operator 1 will complete a Post-Study Survey of Site Operator 1.
- A site operator will label one (1) EDTA/lavender-top tube with participant ID using labels printed in advance of study.
- A healthcare professional with appropriate phlebotomy training, using standard phlebotomy procedures, will collect one tube of blood from the participant (one EDTA/lavender-top tube), then gently invert the tube eight (8) times immediately to evenly distribute the additive.
- Site operator 2, blinded to the result of site operator 1, will read the Transfer Device Method (Waived) Instructions For Use and perform the ADEXUSDx® COVID-19 Test according to the instructions using blood from the EDTA/lavender-top tube.
- Site operator 2 will complete a Case Report Form of Site Operator 2.
- Site operator 2 will complete a Post-Study Survey of Site Operator 2.
- A trained laboratorian will prepare the sample for shipment according to the following specimen handling instructions:
  - For the EDTA/lavender-top tube:
    - *Note: Must be maintained at 2-8°C while handling.*
    - Centrifuge at high speed for 10-15 minutes, then immediately pipette the plasma into a transport tube.
    - Label the tube with subject ID, write 'Plasma' on the tube, ensure the cap is screwed on tight, and wrap in parafilm.
    - Store at -20°C for frozen shipment to NOWDx.
- The participant will return their demographic survey to a site operator.
- A site operator will complete a study visit checklist and incentive receipt form and obtain the signature of the participant.
- The participant will be compensated \$50 by a site operator.

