- A positive COVID-19 result with a NOWDx COVID-19 Test may be an indicator of an active or past SARS-CoV-2 infection. Participants with positive results will be referred for follow-up with their healthcare provider.
- All study forms will be sent to NOWDx daily.
- All remaining samples will be bulk shipped to NOWDx at the conclusion of the study for further testing as needed.

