## Statistical Considerations

The study is designed to support POC EUA of the ADEXUSDx® COVID-19 Test. Clinical study data will be analyzed to assess the performance of the NOWDx COVID-19 Test. Specifically, specificity and sensitivity of the NOWDx COVID-19 Test will be determined relative to an emergency use authorized molecular (PCR) assay. The data must demonstrate a minimum overall 90% positive percent agreement (PPA) and overall 95% negative percent agreement (NPA) with point estimates not lower than 90% for combined PPA and not lower than 93% for combined NPA.

All data will be subject to performance of routine interim analyses. Results from interim analyses will help determine if the clinical trial needs to be halted due to study performance problems.

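### The PCR-negative cohort has no exclusion for an earlier positive PCR, so a recovered person's correct antibody result can count as a false positive

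*Protocol*

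**What the plan says.** Protocol, Clinical Study Cohorts, defines two groups of 30. The negative cohort's entry rule begins "Inclusion criteria: Persons who have tested negative for COVID-19 with an emergency use authorized molecular (PCR) test and can furnish said test report", with a window of 0 to 6 days after the test. Besides age under 18 and limited reading skills, its exclusions are "persons who have previously participated in a NOWDx study; > 6 days post emergency use authorized molecular (PCR) test". The positive cohort's rule begins "Inclusion criteria: Persons who have tested positive for COVID-19 with an emergency use authorized molecular (PCR) test and can furnish said test report", with the test at least 7 days earlier. Neither list says what to do with a person who has both a positive and a negative report, and neither says which PCR test the day limits refer to.

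Background Information and Rationale says the device "identifies total immunoglobulin (IgM, IgG, and IgA) to SARS-CoV-2". Study Procedures says a positive device result "may be an indicator of an active or past SARS-CoV-2 infection". Statistical Considerations measures sensitivity and specificity against PCR. It asks for 90% overall positive percent agreement (PPA) and 95% overall NPA, with point estimates "not lower than 90% for combined PPA and not lower than 93% for combined NPA". Study Procedures also notes: "Specific cohort assignment will not be made until study visit is complete". No rule follows for a person who fits both cohorts.

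**The concern.** PCR shows whether virus is detectable now. The device shows whether antibody is present, which by the protocol's own account can come from a past infection. Someone with a positive PCR some weeks ago and a negative PCR this week is PCR-negative but may well carry antibody. If that person is counted in the negative cohort, the device is marked wrong for being right.

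Recruitment makes such people plausible, because the study seeks both those who have tested positive and those with a recent negative test. The stake is the NPA result. With 30 negatives, one or two misplaced people use up the whole allowance for false positives. A sound device could then miss its target, or the study could be stopped for poor correlation at an interim analysis, which the protocol lists as a ground for early termination.

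**Working it through.** **Reproducing the plan's figure.** The cohorts are 30 and 30, and 30 + 30 = 60, which agrees with "Total planned enrollment is 60 study participants". The protocol shows no power calculation, so there is nothing more to reproduce.

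**Who can enter.** Take a person with a positive PCR at least 7 days old and a negative PCR 0 to 6 days old. The outcome depends on which test the day limits mean:

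| Day limits refer to | Negative cohort | Positive cohort |
|---|---|---|
| The furnished report | eligible | eligible |
| The latest PCR test | eligible | excluded |
| Any PCR test | excluded | excluded |

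The first reading is the natural one, because the limits follow directly on the report to be furnished. On the first two readings the person can be scored as a negative.

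**What the limits allow.** 29/30 = 96.7%, 28/30 = 93.3% and 27/30 = 90.0%. The 95% figure therefore permits one false positive and the 93% floor permits two.

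**Perfect device.** Let k be the number of recovered, antibody-positive persons in the negative cohort.
- k = 1: 29/30 passes both limits but uses up one permitted false positive.
- k = 2: 28/30 fails 95% and passes 93%.
- k = 3: 27/30 fails both.

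If the combined NPA pools the two sampling methods (60 readings from 30 people) and both methods detect the antibody, the results are 58/60, 56/60 and 54/60. The limits are then 57/60 (95%) and 56/60 (93%), so each case passes or fails as before.

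**Imperfect device.** These values are assumed, not taken from the documents: sensitivity 0.95 (also in recovered persons), specificity 0.98, one sampling method.

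False positives = Binomial(30 − k, 1 − specificity) + Binomial(k, sensitivity).

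- k = 0, at most one: 0.98^30 + 30 × 0.02 × 0.98^29 = 0.545 + 0.334 = 0.880 (unrounded terms).
- k = 1, at most one: 0.95 × 0.98^29 + 0.05 × (0.98^29 + 29 × 0.02 × 0.98^28) = 0.95 × 0.557 + 0.05 × 0.886 = 0.573.
- k = 2, at most one: 2 × 0.95 × 0.05 × 0.98^28 + 0.05² × (0.98^28 + 28 × 0.02 × 0.98^27) = 0.095 × 0.568 + 0.0025 × 0.893 = 0.056.

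The joint chance multiplies by the chance that PPA reaches 27/30, which is 0.939 at sensitivity 0.95.

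| k | NPA ≥ 95% | NPA ≥ 93% | PPA and NPA ≥ 95% | PPA and NPA ≥ 93% |
|---|---|---|---|---|
| 0 | 0.880 | 0.978 | 0.826 | 0.919 |
| 1 | 0.573 | 0.891 | 0.538 | 0.837 |
| 2 | 0.056 | 0.600 | 0.053 | 0.563 |

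**Sensitivity to the assumptions.** Joint chance with no such person, then with one:

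| Sensitivity | Specificity | 95% NPA | 93% NPA |
|---|---|---|---|
| 0.95 | 0.97 | 73% to 41% | 88% to 74% |
| 0.95 | 0.99 | 91% to 71% | 94% to 91% |
| 0.95 | 1.00 | 94% to 94% | 94% to 94% |
| 0.90 | 0.98 | 57% to 38% | 63% to 58% |
| 0.99 | 0.98 | 88% to 56% | 98% to 89% |

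**The case against.** The strongest objection is that every probability depends on k, which the documents do not give. To do harm, a person must have had a positive PCR, been retested, been negative within six days, and then been enrolled on the negative report although the positive one also qualifies. With k = 0 nothing happens. With k = 1 and specificity 100%, nothing changes either. This stands, and it is why no expected loss is stated.

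Second, the error is conservative: it lowers NPA and so does not flatter the device. That is largely true. The reverse error, a missed antibody scored as a true negative, has a 5% chance per such person at 95% sensitivity. But an NPA that understates specificity is still a wrong estimate.

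Third, a PCR comparator is what the guidance described in the Background calls for, and past infection never tested by PCR would be scored the same way. Both are correct. The proposal keeps the comparator and removes only people whose own PCR history contradicts the label.

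Fourth, the matter may be handled elsewhere. The exclusion for more than 6 days since PCR could cover any PCR test, but that would also bar anyone with an older negative test. The phone script (Appendix B, not shown) may ask about earlier tests, but the criteria themselves give no ground for declining the person. The section Retaining Samples allows plasma to be retested after a discrepant result, but gives no rule for reclassifying the participant.

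Finally, the tabulated chances are for one method, while the floors apply to combined figures. Pooling was checked only for the case where both methods detect the antibody in every such person and nobody else is positive. There it changes no pass or fail.

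**Conclusion.** The concern holds. On its natural reading, the eligibility text lets a person with a documented past infection count as a negative for an antibody test, and the analysis then scores a correct result as an error. The arithmetic for a perfect device needs no assumption beyond the number of such persons: two are enough to fail the 95% figure and three to fail the 93% floor. With 95% sensitivity and 98% specificity assumed, one such person cuts the chance of meeting the NPA limit from 88% to 57% (95%) or from 98% to 89% (93%).

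The number who would enrol is unknown and the bias runs mainly against the sponsor. This is therefore a change that should be made, not one on which the study stands or falls.

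**What to change.** In Clinical Study Cohorts, add two statements:

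1. A person with a known earlier positive PCR is excluded from the negative cohort.
2. The 0-to-6-day and 7-day limits refer to the furnished report.

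A person with both reports could then enter only the positive cohort, which also settles the overlap. If Appendix B does not already ask about earlier positive tests, add one screening question.

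The cost is small. A few otherwise eligible negatives would be declined and replaced within the six-week period from July 20 to August 31, 2020. Sample size and operator masking do not change. The exclusion relies on what the person reports, since only one PCR report must be furnished, and it does not remove past infection that was never PCR-tested.

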## **Study Design**

### **Recruitment, Screening, Consent, and Enrollment**

Recruitment materials for this study (flyers, social media advertisements, and classified website advertisements) may be used to direct interested participants to the study sites for screening. See **Appendix A. Recruitment Materials**. Designated operators will screen each interested person via telephone for potential eligibility using a script. See **Appendix B. Phone Screening Script and FAQ**. Phone Screening Script responses will be recorded. If qualified, persons will be identified by designated operators as eligible for enrollment in a study cohort. Screened and eligible persons will be directed to a study site for enrollment. Enrollment eligibility information shared with site operators who will perform the study will be limited to general eligibility for the 'Clinical Study'. Specific cohort eligibility information will not be shared with site operators who will perform the study. At an active study site, a site operator will review the IRB-approved protocol and initiate the informed consent process. The formal consent of each participant, using the IRB-approved consent form, will be obtained before the participant engages in any study procedure. All prospective participants for the study will be provided with a consent form describing this study and will be given sufficient information in language suitable for persons to make an informed decision about their participation in the study. The site operator obtaining consent will thoroughly explain each element of the document including the purpose and requirements of the study. The consent process will take place in a quiet and private room or space, and persons may take as much time as needed to decide about their participation. Privacy will be maintained and questions regarding participation will be answered. No coercion or undue influence will be used in the consent process. The participant will be informed of any risks or discomforts he or she may experience during the study conduct. The consent form must be signed and dated by the participant. A copy of the signed and dated consent will be given to the participant, and the informed consent process will be documented in each participant's research record. A statement offering the participant the opportunity to withdraw from the study at any time without consequences will be provided. If the person declines consent, they will not be enrolled in the study. All consenting persons will be enrolled as participants.

### **Study Procedures**

Herein, we present study procedures for the 'Clinical Study':

Title: NOWDx COVID-19 EUA Blood Test CLIA Waiver Trial

Sponsor: NOWDiagnostics, Inc.

- Site operator 1 will create a participant ID.  
*Note: Specific cohort assignment will not be made until study visit is complete.*
- Site operator 1 will provide the participant with a demographic survey to complete (see **Appendix C. Demographic Survey of Participant**). Participant will complete the survey.
- Site operator 1 will read the Finger Stick Method (Waived) Instructions For Use and perform the ADEXUSDx® COVID-19 Test on the participant according to the instructions.
- Site operator 1 will complete a Case Report Form of Site Operator 1.
- Site operator 1 will complete a Post-Study Survey of Site Operator 1.
- A site operator will label one (1) EDTA/lavender-top tube with participant ID using labels printed in advance of study.
- A healthcare professional with appropriate phlebotomy training, using standard phlebotomy procedures, will collect one tube of blood from the participant (one EDTA/lavender-top tube), then gently invert the tube eight (8) times immediately to evenly distribute the additive.
- Site operator 2, blinded to the result of site operator 1, will read the Transfer Device Method (Waived) Instructions For Use and perform the ADEXUSDx® COVID-19 Test according to the instructions using blood from the EDTA/lavender-top tube.
- Site operator 2 will complete a Case Report Form of Site Operator 2.
- Site operator 2 will complete a Post-Study Survey of Site Operator 2.
- A trained laboratorian will prepare the sample for shipment according to the following specimen handling instructions:
  - For the EDTA/lavender-top tube:
    - *Note: Must be maintained at 2-8°C while handling.*
    - Centrifuge at high speed for 10-15 minutes, then immediately pipette the plasma into a transport tube.
    - Label the tube with subject ID, write 'Plasma' on the tube, ensure the cap is screwed on tight, and wrap in parafilm.
    - Store at -20°C for frozen shipment to NOWDx.
- The participant will return their demographic survey to a site operator.
- A site operator will complete a study visit checklist and incentive receipt form and obtain the signature of the participant.
- The participant will be compensated \$50 by a site operator.
- A positive COVID-19 result with a NOWDx COVID-19 Test may be an indicator of an active or past SARS-CoV-2 infection. Participants with positive results will be referred for follow-up with their healthcare provider.
- All study forms will be sent to NOWDx daily.
- All remaining samples will be bulk shipped to NOWDx at the conclusion of the study for further testing as needed.

## Statistical Considerations

The study is designed to support POC EUA of the ADEXUSDx® COVID-19 Test. Clinical study data will be analyzed to assess the performance of the NOWDx COVID-19 Test. Specifically, specificity and sensitivity of the NOWDx COVID-19 Test will be determined relative to an emergency use authorized molecular (PCR) assay. The data must demonstrate a minimum overall 90% positive percent agreement (PPA) and overall 95% negative percent agreement (NPA) with point estimates not lower than 90% for combined PPA and not lower than 93% for combined NPA.

All data will be subject to performance of routine interim analyses. Results from interim analyses will help determine if the clinical trial needs to be halted due to study performance problems.

## Study Administration

### **Data Collection and Management**

A data management plan (DMP) will serve as an outline for how data are to be handled during the study and after the study is completed.

Each study site PI will carefully monitor study procedures to protect the safety of study participants, the quality of the data, and the integrity of the study. All participant study materials will be assigned a unique identifying code called a Participant ID. The key to the code will be kept in a password protected file for the duration of the study. Only IRB approved study personnel at the Sponsor and the study site will have access to the code and information that identifies site specific study participants.

Paper or electronic study documents may be used in this study. Site operators will be given detailed operator instructions. All paper study documents must be scanned and emailed daily to [[contact]](mailto:[contact]). If internet connectivity is impaired, paper forms may be faxed to [contact] initially, then scanned and emailed upon reactivation of internet connection.

All paper study documents received from the sites will be stored on Microsoft SharePoint. Data will be entered into the database and are subject to independent data entry review at the time of data entry and during database audits. All EUA molecular (PCR) test reports received will be stored on Microsoft SharePoint. These data are also subject to independent data entry review at the time of data entry and during database audits.

Database audits will be performed bi-weekly and prior to performance of biweekly interim analyses to ensure reconciliation of relevant data (e.g. survey data, other relevant study forms).

The FDA and local regulatory authorities may inspect all study documents. If any results of the study are published, participant data will be de-identified.

